2.1.1.9 The effects of the immunotherapies (PRGN-2009 vaccine and M7824) on the developing human fetus are unknown. For this reason and because M7824 and PRGN-2009 used in this trial are possibly teratogenic, women of child-bearing potential and men must agree to use highly effective contraception (hormonal or barrier method of birth control;

abstinence) prior to study entry and up to 2 months following the last dose of M7824 study treatment. Should a woman become pregnant or suspect she is pregnant while she or her partner is participating in this study, she should inform her treating physician immediately.

2.1.1.10 Participants serologically positive for HIV, Hep B, Hep C are eligible as long as the viral loads are undetectable by quantitative PCR. HIV positive participants must have CD4 count ≥ 200 cells per cubic millimeter at enrollment, be on stable antiretroviral therapy for at least 4 weeks and have no reported opportunistic infections or Castleman's disease within 12 months prior to enrollment.

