2.1.2 Exclusion Criteria

2.1.2.1 Participants with prior investigational drug, live vaccine, chemotherapy, immunotherapy or any prior radiotherapy (except for palliative bone directed therapy) within the past 28 days prior to the first drug administration except if the investigator has assessed that all residual treatment-related toxicities have resolved or are minimal and feel the participant is otherwise suitable for enrollment. Participants may continue adjuvant hormonal therapy in the setting of a definitively treated cancer (e.g., breast).

2.1.2.2 Major surgery within 28 days prior to the first drug administration (minimally invasive procedures such as diagnostic biopsies are permitted).

2.1.2.3 Known active brain or central nervous system metastasis (less than a month out from definitive radiotherapy or surgery), seizures requiring anticonvulsant treatment (<3 months) or clinically significant cerebrovascular accident (<3 months). In order to be eligible participants must have repeated CNS imaging at least a month after definitive treatment showing stable CNS disease. Participants with evidence of intratumoral or peritumoral hemorrhage on baseline imaging are also excluded unless the hemorrhage is grade ≤ 1 and has been shown to be stable on two consecutive imaging scans.

2.1.2.4 Pregnant women are excluded from this study because M7824 and PRGN-2009 vaccine have not been tested in pregnant women and there is potential for teratogenic or abortifacient effects. Because there is an unknown but potential risk for adverse events in nursing infants secondary to treatment of the mother with these immunotherapies, breastfeeding should be discontinued if the mother is treated on this protocol.

2.1.2.5 Only for Phase I, Arm 1B: Active autoimmune disease that might deteriorate when receiving an immunostimulatory agent with exception of:

- Diabetes type I, eczema, vitiligo, alopecia, psoriasis, hypo- or hyperthyroid disease or other mild autoimmune disorders not requiring immunosuppressive treatment;
- Administration of steroids for other conditions through a route known to result in a minimal systemic exposure (topical, intranasal, intro-ocular, or inhalation) is acceptable;

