3.2.2 M7824

Subjects enrolled to Arm 1B will receive M7824 via IV infusion over 1 hour (-10 minutes / +20 minutes, that is, over 50 to 80 minutes) once every 2 weeks for up to a year (Arm 1B). M7824 will be administered as a "flat" dose of 1,200 mg independent of body weight. M7824 is administered as an intravenous infusion with a mandatory 0.2 micron in-line filter. Infusion of M7824 can be administered through a PIV or CVAD or port with titanium as the main material.

Current experience revealed that IRRs to M7824 occur seldomly and are generally mild to moderate in severity. Therefore, administration of a premedication is generally not required.

In order to mitigate potential infusion-related reactions, premedication with an antihistamine and with acetaminophen (for example, 25-50 mg diphenhydramine and 500-650 mg acetaminophen) within approximately 30 to 60 minutes prior to dosing of M7824 is optional and at the discretion of the Investigator.

Management of symptoms should follow the guidelines shown in **Table 2**.

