3.4 STUDY CALENDAR

3.4.1 Study Calendar for Phase I

Procedure	Screening ¹	Baseline / Day 1 ²	Odd numbered Weeks (W1, W3, W5, W7 onwards) ³	EOT ⁴	Safety follow up ⁵	Long Term follow up ⁶
Treatment ³		X	X			
NIH Advance Directives Form ⁷		X				
Medical History ¹⁷	X					
Height	X					
Physical exam, weight, vital signs, ECOG ¹⁶	X	X	X	X	X	
Skin assessment ¹⁸		X	X	X	X	
HIV, HCV, HepB	X					
EKG	X			X	X	
CBC with differential	X	X	X	X	X	
Biochemical profile ⁸	X	X	X	X	X	
Tumor Markers ⁹		X	X	X		
CD4 ¹⁰	X					
TSH with reflex Free T3 and T4, lipase, amylase, CRP		X	X ¹¹			
Urinalysis	X					
Urine or serum pregnancy testing in women of childbearing potential	X	X	X			
PT, INR, PTT		X				
Tumor evaluation (CT Scan / MRI)	X	X	X ¹²			X
Brain CT/MRI ¹³	X					
Concomitant Medications		X	X	X	X	
Adverse events		X	X	X	X	
Biopsy for immune analysis ¹⁴		X	X			
Research Blood ¹⁵		X	X	X		
Telephone Follow Up					X	X

1. Screening evaluations performed within 28 days prior to the first drug administration, unless specified in Section **2.2**.

2. Baseline evaluations performed within 2 weeks prior to first drug administration.

Note: Baseline Labs will not be redrawn if done already as screening within the 2 weeks prior to drug administration.

3. Treatment:

- Trial treatment will be given with either HPV vaccine monotherapy (Arm 1A) or the combination of HPV vaccine + M7824 (Arm 1B) for a year.
- HPV vaccine will be given on D1, D15 and D29 followed by every 4 weeks thereafter and M7824 will be given every 2 weeks.
- Both of these agents may be discontinued early for unacceptable toxicity or disease progression. Treatment beyond a year may be given per PI discretion.
- Administration of study agents and indicated evaluations can be done up to 14 days earlier or delayed up to 14 days due to holidays, inclement weather, conflicts, or similar reasons.

The timing of subsequent administrations is adjusted to maintain a minimum of 11 days between treatments of similar agents.

4. EOT – End of treatment visit: Where feasible, on the day of or within 7 days of the decision to discontinue treatment prematurely before completion of one year of treatment.

5. Approximately 28 days (+/- 7 days) after last treatment. If subjects are not willing to come to NIH for FU visit, they will be contacted by phone to assess adverse events and for such participants no labs will be needed at FU.

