3.4.2 Study Calendar for Phase II

Procedure	Screening ¹	Baseline ²	Week 1	Week 3	Week 4-5 ¹⁸	EOT ⁴	Safety follow up ⁵	Long Term follow up ⁶
Biochemical profile ⁸	X	X	X	X	X	X	X	
CD4 ⁹	X							
TSH with reflex Free T3 and T4, lipase, amylase, CRP		X	X	X	X			
Urinalysis	X							
Urine or serum pregnancy testing in women of childbearing potential	X	X	X	X				
HLA typing ¹⁷		X						
PT, INR, PTT		X						
Tumor evaluation (CT Scan / MRI) ¹⁰	X	X			X			
Concomitant Medications		X	X	X	X	X	X	
Adverse events		X	X	X	X	X	X	
Biopsy for immune analysis ¹¹		X			X			
Research Blood ¹²		X	X	X	X	X		
Saliva sample ¹⁵		X	X	X	X	X	X	
Taken off treatment for definitive treatment ¹⁹					X			
Telephone/email Follow Up							X	X

1. Screening evaluations performed within 28 days prior to the first drug administration, unless specified in Section [2.2](#).

2. Baseline evaluations performed within 2 weeks prior to first drug administration.

Note: Baseline Labs will not be redrawn if done already as screening within the 2 weeks prior to drug administration.

Note: Imaging within 4 weeks prior to drug administration.

3. Therapeutic agents administered will be as outlined in Section [3.1](#):

- Participants will be planned to receive two doses of treatment (HPV vaccine alone in Arm 2A) before definitive standard of care therapy.
- Administration of study agents and indicated evaluations can be done up to 3 days earlier or delayed up to 3 days due to holidays, inclement weather, conflicts, or similar reasons.

The timing of subsequent administrations is adjusted to maintain a minimum of 11 days between treatments of similar agents.

4. EOT – End of treatment visit: Where feasible, on the day of or within 7 days of the decision to discontinue treatment prematurely before completion of one year of treatment prematurely or one month of neoadjuvant or induction treatment. Note: Does not need to be completed if drug is withheld after these timepoints and such participants will be considered off-treatment.

5. Approximately 28 days (+/- 7 days) after last treatment. If subjects are not willing to come to NIH for FU visit, they will be contacted by phone to assess adverse events and for such participants no labs will be needed at FU.

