8.6.2 Paternal Exposure

Male participants should refrain from fathering a child or donating sperm during the study and for two months after the last dose of M7824.

Pregnancy of the participant's partner is not considered to be an AE. The outcome of all pregnancies occurring from the date of the first dose until 2 months after the last dose should, if possible, be followed up and documented. Pregnant partners may be offered the opportunity to participate in an institutional pregnancy registry protocol (e.g., the NIH IRP pregnancy registry study) to provide data about the outcome of the pregnancy for safety reporting purposes.

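### Criterion 2.1.1.9 counts the end of contraception from the last M7824 dose, so it sets no usable stop date for vaccine-only participants

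*Combined protocol and SAP*

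**What the plan says.** Criterion 2.1.1.9 gives its reason and its duty in one sentence: "because M7824 and PRGN-2009 used in this trial are possibly teratogenic, women of child-bearing potential and men must agree to use highly effective contraception". The period is "prior to study entry and up to 2 months following the last dose of M7824 study treatment". The criterion carries no phase or arm restriction. Exclusion criterion 2.1.2.4 repeats the fetal concern for both agents: "M7824 and PRGN-2009 vaccine have not been tested in pregnant women and there is potential for teratogenic or abortifacient effects".

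Section 8.6.2 adds a rule for men: "Male participants should refrain from fathering a child or donating sperm during the study and for two months after the last dose of M7824". Its next paragraph asks for follow-up of partner pregnancies over a window that names no agent: "The outcome of all pregnancies occurring from the date of the first dose until 2 months after the last dose".

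On who receives M7824, section 3.2.2 states: "Subjects enrolled to Arm 1B will receive M7824 via IV infusion over 1 hour". The Phase I calendar (3.4.1, note 3) describes Arm 1A as vaccine monotherapy. For Phase II, note 3 of 3.4.2 states: "Participants will be planned to receive two doses of treatment (HPV vaccine alone in Arm 2A) before definitive standard of care therapy". The note in 1.2.9 records that Arm 2B, the Phase II combination arm, was closed before enrolment began.

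**The concern.** The reason for the rule covers two agents, but the clock runs on one of them. A participant who never receives M7824 has no last M7824 dose, so the two-month period has no starting point. The criterion then does not say when a vaccine-only participant may stop contraception, although the protocol treats the vaccine as a possible fetal hazard.

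What is at stake is the period after the last vaccine dose. In the Phase II calendar, pregnancy tests are marked at screening, baseline, Week 1 and Week 3. The second and last dose is on D15, which falls in Week 3, and no test is marked after that. Once dosing ends, the contraception rule is therefore the main protection, and its end is the part that is missing.

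**Working it through.** The plan has no figure to reproduce. The check compares the rule with the arms, looks for a substitute end point elsewhere, and then counts the participants affected.

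**1. End point of 2.1.1.9 by arm**

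| Arm | Agents | Last M7824 dose exists? | Stop date under 2.1.1.9 |
|---|---|---|---|
| 1A (closed) | PRGN-2009 | No | None usable |
| 1B | PRGN-2009 + M7824 | Yes | 2 months after it |
| 2A (all of Phase II) | PRGN-2009 | No | None usable |
| 2B | PRGN-2009 + M7824 | Closed, never enrolled | Not applicable |

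**2. Is the M7824 anchor deliberate scoping?** Where the protocol limits a criterion, it says so. Criteria 2.1.2.5 and 2.1.2.9 are limited to Phase I Arm 1B, 2.1.2.6 and 2.1.2.7 to Phase I, and 2.1.2.11 to participants who may receive M7824. Criterion 2.1.1.9 has no such limit and names the vaccine in its reason. Wording left over from when M7824 was planned for Phase II is a likely cause, but that is an inference.

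**3. Does another section supply an end point?**
- *Women.* Section 8.6.1 deals with a pregnancy that occurs during the study and stops treatment. Section 3.6.1 removes a participant with a positive test from therapy. Neither sets a contraception period.
- *Men.* Section 8.6.2 joins two periods: the time on study, and two months after M7824. For a man who never receives M7824 the second part is empty, but the first remains. In Phase II, section 3.6.2 ends study participation at completion of the 5-year follow-up unless an earlier off-study event occurs. The period is therefore bounded, but it may be very long.
- *Partner pregnancies.* The agent-neutral window in 8.6.2 governs follow-up of outcomes. It suggests the intended anchor but imposes no contraception.

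**4. Arm 1B.** The treatment-duration paragraph in 3.1.1 lets a tolerated single agent continue after the other is stopped. Boosters are every 4 weeks and M7824 every 2 weeks (3.2.1, 3.2.2). Taking 2 months as 61 days, on the nominal schedule during the booster phase:
- If the last M7824 dose coincides with a booster, later boosters fall at 28, 56 and 84 days. The third is after day 61.
- If it falls midway between boosters, they fall at 14, 42 and 70 days. Again the third is after day 61.

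A woman kept on vaccine for three further boosters would thus pass the 2.1.1.9 end point while still being vaccinated. A man would still be on study and covered by 8.6.2.

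**5. Reach.** From Table 8 (section 14.1.2), whose arms match this trial:
- Treated: 3 + 3 + 11 + 22 = 39.
- Vaccine only: 3 + 3 + 22 = 28, and 28/39 = 71.8%.
- Phase II: 22 treated, against 20 + up to 2 = up to 22 planned evaluable (10.2).
- Arm 1B: 11 treated, against a target of 10 evaluable.
- Places under the ceiling: 50 − 39 = 11, which 10.2 reserves for a few inevaluable participants.

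**The case against.** The strongest reply is that the gap is narrow. The act required at entry, agreeing to highly effective contraception, can be applied to everyone; only the stop date is unclear. Pregnant women are excluded, tests are repeated during treatment, and pregnancy ends treatment. The consent pages, which would normally tell participants the period, are not visible here, and their absence cannot count against the plan. This stands. It rules out saying that the whole rule is unworkable or that staff were left to guess.

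A reader might also infer that 8.6.2 leaves vaccine-only men with no defined period. The text does not support that, because the on-study clause still binds them. The same clause defeats the Arm 1B scenario for men. What remains for men is a mismatch: 8.6.2 may run to the end of a five-year follow-up, while 2.1.1.9 gives them no usable end.

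The 72% should not be read as the share exposed to fetal risk. It counts everyone treated with vaccine alone, and the documents do not say for how many contraception was relevant. The match of 22 treated with 20 + 2 planned is only a match of totals: Table 8 counts treated participants, the plan counts evaluable ones, and the table does not separate oropharyngeal from sinonasal cases.

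None of this supplies a stop date for vaccine-only women.

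**Conclusion.** The point holds for 2.1.1.9. The criterion applies to all arms, cites possible teratogenicity of both agents, and counts its end from a drug that vaccine-only participants never receive. No other visible section gives women a contraception end point counted from PRGN-2009. In Arm 1B the rule could lapse for a woman during continued vaccination; this is possible under the text, and nothing shows that it occurred. For men the defect is inconsistency between two sections, not a missing period.

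Severity is minor. The affected group is 28 of 39 treated participants in Table 8, with an unknown number for whom contraception matters and apparently little enrolment left. No endpoint, sample size or analysis changes. The conclusion rests on the visible protocol text; the consent form may already state a period.

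**What to change.** In 2.1.1.9, change the anchor to *last dose of study treatment (PRGN-2009 or M7824, whichever is later)*, and use the same anchor in the first sentence of 8.6.2. This agrees with the agent-neutral window already used for partner pregnancies.

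The sponsor should also:
- confirm that two months suits the vaccine, since the documents give no basis for that length for PRGN-2009;
- state whether the on-study clause in 8.6.2 includes long-term follow-up;
- align the consent text.

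The cost is one phrase in two sections, a clarification in 8.6.2 and a consent check. Visits, endpoints, sample size and analysis stay as they are.

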2.1.2 Exclusion Criteria

2.1.2.1 Participants with prior investigational drug, live vaccine, chemotherapy, immunotherapy or any prior radiotherapy (except for palliative bone directed therapy) within the past 28 days prior to the first drug administration except if the investigator has assessed that all residual treatment-related toxicities have resolved or are minimal and feel the participant is otherwise suitable for enrollment. Participants may continue adjuvant hormonal therapy in the setting of a definitively treated cancer (e.g., breast).

2.1.2.2 Major surgery within 28 days prior to the first drug administration (minimally invasive procedures such as diagnostic biopsies are permitted).

2.1.2.3 Known active brain or central nervous system metastasis (less than a month out from definitive radiotherapy or surgery), seizures requiring anticonvulsant treatment (<3 months) or clinically significant cerebrovascular accident (<3 months). In order to be eligible participants must have repeated CNS imaging at least a month after definitive treatment showing stable CNS disease. Participants with evidence of intratumoral or peritumoral hemorrhage on baseline imaging are also excluded unless the hemorrhage is grade ≤ 1 and has been shown to be stable on two consecutive imaging scans.

2.1.2.4 Pregnant women are excluded from this study because M7824 and PRGN-2009 vaccine have not been tested in pregnant women and there is potential for teratogenic or abortifacient effects. Because there is an unknown but potential risk for adverse events in nursing infants secondary to treatment of the mother with these immunotherapies, breastfeeding should be discontinued if the mother is treated on this protocol.

2.1.2.5 Only for Phase I, Arm 1B: Active autoimmune disease that might deteriorate when receiving an immunostimulatory agent with exception of:

- Diabetes type I, eczema, vitiligo, alopecia, psoriasis, hypo- or hyperthyroid disease or other mild autoimmune disorders not requiring immunosuppressive treatment;
- Administration of steroids for other conditions through a route known to result in a minimal systemic exposure (topical, intranasal, intro-ocular, or inhalation) is acceptable;
- Subjects on systemic intravenous or oral corticosteroid therapy with the exception of physiologic doses of corticosteroids (\leq the equivalent of prednisone 10 mg/day) or other immunosuppressors such as azathioprine or cyclosporin A are excluded on the basis of potential immune suppression. For these subjects these excluded treatments must be discontinued at least 1 weeks prior to enrollment for recent short course use (≤ 14 days) or discontinued at least 4 weeks prior to enrollment for long term use ($>$

14 days). In addition, the use of corticosteroids as premedication for contrast-enhanced studies is allowed prior to enrollment and on study.

- 2.1.2.6 Only for Phase I: Subjects with a history of serious intercurrent chronic or acute illness, such as cardiac or pulmonary disease, hepatic disease, bleeding diathesis or recent (within 3 months) clinically significant bleeding events, known left ventricular ejection fraction <50% (confirmation of EF > 50% is not required for eligibility), history of myocarditis, or recent myocardial infarction (within 6 months), or other illness considered by the Investigator as high risk for M7824 drug treatment.
- 2.1.2.7 Only for Phase I: Subjects refusing to accept blood products as medically indicated.
- 2.1.2.8 History of second malignancy within 3 years of enrollment except for the following: adequately treated localized skin cancer, cervical carcinoma in situ, superficial bladder cancer, other localized malignancy which has been adequately treated or malignancy which does not require active systemic treatment (e.g., low risk CLL). For participants enrolled on the phase I portion of the protocol a second HPV driven malignancy is allowed.
- 2.1.2.9 Only for Phase I, Arm 1B: Subjects with a known severe hypersensitivity reaction to monoclonal antibodies or its excipients (grade >/= 3 NCI-CTCAE v5) will be evaluated by the allergy/immunology team prior to enrollment.
- 2.1.2.10 Prior allogenic tissue/solid organ transplant.
- 2.1.2.11 For participants who may receive M7824: previous life-threatening side effects resulting from prior checkpoint inhibitor therapy.
- 2.1.2.12 Participants with pulse oximetry < 92% on room air at screening.
- 2.1.2.13 Participants unable to provide informed consent.
- 2.1.2.14 Participants whose inclusion in the trial would in the judgement of the PI lead to time from diagnosis to initiation of curative treatment of >70 days (Arm 2A only).

2.1.3 Recruitment Strategies

This protocol may be abstracted into a plain language announcement posted on NIH websites and on NIH social media platforms.

This study will be listed on www.clinicaltrials.gov. This study may be advertised at national conferences including AACR and ASCO and may also be shared with the HPV and Anal Cancer Foundation who may advertise it further. Recruitment flyers may be used to advertise this study in the future after IRB approval.

Participants for the Phase I portion of the study will be recruited from the current participant population at NIH. participants with HPV related cancers are currently being treated on another trial through LTIB, CCR, NIH, where 2-3 participants per month are being screening and enrolled. Some of these participants come from established community networks, some of these participants are self-referrals, and some of these participants are referred by another group ([name] group, Experimental Transplantation and Immunology Branch, CCR, NIH) who also have a large referral base for HPV related cancers. Participants on the phase II portion of the study will be recruited from locoregional hospital including the Johns Hopkin's community network of which [name], an AI on this protocol, is also a part.

2.2 SCREENING EVALUATION

2.2.1 Screening activities performed prior to obtaining informed consent

Minimal risk activities that may be performed before the subject has signed a consent include the following:

- Email, written, in person or telephone communications with prospective subjects.
- Review of existing medical records to include H&P, laboratory studies, etc.
- Review of existing MRI, x-ray, or CT images.
- Review of existing photographs or videos.
- Review of existing pathology specimens/reports from a specimen obtained for diagnostic purposes.

